4.2 Primary endpoint OS

OS is the primary endpoint for this study. It is defined as the time from the date of randomization to the date of death due to any cause in all randomized subjects. Subjects who are alive will be censored at the last known alive dates.

On treatment visits will occur at Day 1 and every 2 weeks thereafter. Subjects will be treated until unacceptable toxicity or disease progression. Following discontinuation of therapy, safety will be assessed through post-treatment Follow Up visit 2 (~ 100 days from last dose). Survival status will be assessed every 3 months after follow up visits are completed, and may be completed via telephone or in person visits. Note after discontinuation of therapy, tumor imaging assessment will continue until disease progression (see schedule of tumor imaging assessment in [Section 4.1.1](#)).

4.3 Secondary endpoints

4.3.1 ORR

The secondary endpoint of ORR is the ORR (see [Section 4.1.1](#)) in all randomized subjects with BOR determined based on BICR-assessed tumor response according to RECIST 1.1.

4.3.2 PFS

The secondary endpoint of PFS is the PFS (see [Section 4.1.2](#)) in all randomized subjects with progression is based on the first documented tumor progression assessed by BICR according to RECIST 1.1 or death.

4.3.3 PD-L1 expression

Definition of PD-L1 expression is described as follows.

PD-L1 expression missing: Subjects without an available tumor biopsy specimen for PD-L1 evaluation will be considered as PD-L1 expression missing.

For subjects with an available tumor biopsy specimen(s), the following will be considered:

PD-L1 expression is defined as the percent of tumor cell membrane staining in a minimum of 100 evaluable tumor cells per Dako PD-L1 IHC assay unless otherwise specified. This is referred

as *quantifiable PD-L1 expression*. If the PD-L1 staining could not be quantified, it is further classifies as:

Indeterminate: Tumor cell membrane staining hampered for reasons attributed to the biology of the tumor biopsy specimen and not because of improper sample preparation or handling

[figure not shown]
Not evaluable: Tumor biopsy specimen was not optimally collected or prepared (e.g. PD-L1 expression is neither quantifiable nor indeterminate)

[figure not shown]
Baseline PD-L1 expression: If more than one tumor biopsy specimen is available, baseline PD-L1 expression will be determined from the most recently collected specimen (prior to randomization) with a quantifiable result. If more than one baseline PD-L1 expression measurement is available at the same day for a subject, the highest baseline PD-L1 expression measurement will be used. If all specimens for a given subject are either indeterminate or not evaluable, then the PD-L1 expression will be considered indeterminate as long as at least one specimen is indeterminate. Otherwise, PD-L1 expression will be considered not evaluable.

PD-L1 status is a dichotomized variable using an X% cut-off for quantifiable PD-L1 expression:

- PD-L1 \geq X %: \geq X % PD-L1 expression
- PD-L1 < X %: < X % PD-L1 expression

Where X% denotes the PD-L1 expression cut-off of 1%. Additional cut off values may also be explored.

5 SAMPLE SIZE AND POWER

The sample size determination of this study is based on OS comparison between subjects randomized to receive nivolumab and sorafenib. With a total of 726 subjects randomized in a 1:1 ratio to receive nivolumab or sorafenib, approximately 91.5% power will be achieved with an overall type I error 0.05. The sample size determination is based on simulation using R v3.2 for OS. Below are details of the sample size determination.

General assumptions:

- There are assumed 39% HCV-infected subjects among all randomized subjects.
- In the sorafenib arm, median OS is 10 months for non-HCV infected and 14 months for HCV infected.
- Exponential distribution is assumed for OS in each randomized arm.

Estimated cumulated enrollment of randomized subjects is summarized in Table 5-1.

Table 5-1: Estimated Cumulative Number of Randomized Patients

Month	1	2	3	4	5	6	7	8	9	10	11	12	13
HCV	6	17	30	45	61	81	105	131	159	188	218	250	282
Non-HCV	9	25	43	67	98	132	170	210	252	297	345	394	444
All	15	42	73	112	159	213	275	341	411	485	563	644	726

[figure not shown]
Sample size determination for OS

Based on simulations under the assumptions stated above, approximately 726 subjects will be randomized and followed until at least 520 OS events are observed in order to provide 91.5% power for a hazard ratio of 0.74 with a two-sided type I error of 0.05. This accounts for a group sequential testing procedure with one interim analysis and one final analysis. The HR of 0.74 corresponds to a 35% increase in the median OS for both non-HCV infected subjects and HCV infected subjects.

The interim analysis will be conducted when 80% OS events are observed. The alpha allocation for the interim and final analyses is based on the Lan-DeMets alpha spending function approach using an O'Brien-Fleming stopping boundary controlling for a two-sided overall type 1 error of 5%. The stopping boundary will depend on the actual number of OS events observed at the time of the interim analysis and the final analysis. However, if the interim analysis is performed exactly when 80% OS events are observed, then 0.024 alpha will be used for the interim analysis and 0.043 alpha will be used for the final analysis.

It is projected that an observed hazard ratio of 0.80 or less would result in a statistically significant improvement of nivolumab at the interim analysis of OS; and an observed hazard ratio of 0.84 or

less would result in a statistically significant improvement of nivolumab at the final analysis of OS.

6 STUDY PERIODS, TREATMENT REGIMENS AND POPULATIONS FOR ANALYSES

6.1 Study Periods

Refer to Core Safety SAP³³ for definitions of baseline period and post baseline period for AEs and evaluations of laboratory tests, pulse oximetry and vital signs.

6.2 Treatment Regimens

The treatment group **as randomized** will be retrieved from the IVRS system:

- Nivolumab 240 mg 30 min IV
- Sorafenib 400 mg PO

The treatment group **as treated** will be the same as the treatment group randomized by IVRS. However, if a subject received the incorrect drug for **the entire period** of treatment, the subject's treatment group will be defined as the incorrect drug the subject actually received.

6.3 Populations for Analyses

All analyses will be performed using the treatment group as randomized (intent-to-treat) with the exception of extent of exposure (dosing) and safety, for which the treatment group as treated will be used. If a subject is randomized to nivolumab and receives at least 1 dose of nivolumab during the study, then the subject's treatment group is considered nivolumab. Similarly, if a subject is randomized to sorafenib and receives at least 1 dose of sorafenib, then the subject's treatment group is considered sorafenib.

When appropriate, the following definitions of different types of subjects will be applied to different populations of interest defined later in this section:

- **Enrolled Subjects:** Subjects who signed an informed consent form and were registered into the IVRS.
- **Randomized Subjects:** Enrolled subjects who were randomized to any treatment group in the study. This is the type of subjects for analyses of study conduct, study population and efficacy.
- **Treated Subjects:** Randomized subjects who received at least one dose of study drug. This is the type of subjects for analyses of exposure and safety.
- **PK Subjects:** Randomized subjects who are dosed with nivolumab and have serum time-concentration data available.
- **Response Evaluable Subjects:** Randomized subjects who have target lesion(s) assessed at baseline and at least one post-baseline timepoint.
- **PD-L1 Quantifiable Subjects:** Randomized subjects with quantifiable baseline PD-L1 expression, which exclude randomized subjects with missing or indeterminate or not evaluable baseline PD-L1 expression (see [Section 4.3.3](#)).

7 STATISTICAL ANALYSES

7.1 General Methods

Unless otherwise noted, the titles in the following subsections describe tabulations of discrete variables, by the frequency and proportion of subjects falling into each category, grouped by treatment (with total). Percentages given in these tables will be rounded and, therefore, may not always sum to 100%. Continuous variables will be summarized by treatment group (with total) using the mean, standard deviation, median, minimum and maximum values. If a missing category is not being presented in the data display, only those subjects with non-missing values for the parameter being assessed are included in the percentage calculation.

Time to event distributions (i.e. PFS, OS, DOR and DDC) will be estimated using the KM method. When appropriate, the median along with the corresponding log-log transformed 95% CI will be estimated. Rates at fixed timepoints (e.g., OS at 12 months) will be derived from the KM estimate along with their corresponding log-log transformed 95% confidence intervals.

Unless otherwise specified, the stratification factors for stratified analysis will be the following ones as entered into the IVRS:

- Etiology (HCV vs non-HCV [ie, HBV and HCC with no history of hepatitis virus infection])
- Vascular invasion and/or extrahepatic spread (present vs absent)
- Geography (Asia vs Non-Asia).

The stratified log-rank test will be performed to test the comparison of time to event distributions (OS and PFS) between two treatment arms.

The stratified hazard ratio between two treatment arms along with CI will be obtained by fitting a stratified Cox model with the treatment group variable as unique covariate.

Confidence intervals for binomial proportions will be derived using the Clopper-Pearson method³⁴.

The difference in rates (e.g., ORR) between the two treatment arms along with their two-sided 95% CI will be estimated using the following Cochran-Mantel-Haenszel (CMH) method of weighting³⁵, adjusting for the stratification factors:

$$\hat{\theta} = \frac{\sum w_i \hat{\theta}_i}{\sum w_i} \sim N \left(\theta, \frac{\sum w_i^2 \left[\frac{p_{ix}(1-p_{ix})}{n_{ix}-1} + \frac{p_{iy}(1-p_{iy})}{n_{iy}-1} \right]}{\left(\sum w_i \right)^2} \right)$$

Where $\hat{\theta}_i = p_{ix} - p_{iy}$ is the rate difference of the i th stratum, $w_i = \frac{n_{ix}n_{iy}}{n_{ix} + n_{iy}}$, and n_{ix} and n_{iy} are the number of subjects randomized to treatments x and y, respectively, in the i th stratum.

Associated odds-ratio will be derived.

P-values other than those provided for the primary endpoint OS and the hierarchical testing of the secondary endpoints ORR and PFS are for descriptive purpose only and not adjusted for multiplicity.

7.2 Study Conduct

7.2.1 Accrual

The accrual pattern will be summarized per country, investigational site and per month for all enrolled subjects. Randomization date, first dosing date, country, investigational site will be presented in a by-subject listing of accrual.

7.2.2 Relevant Protocol Deviations

The relevant protocol deviations will be summarized for all randomized subjects, by treatment group and overall. The following programmable deviations from inclusion and exclusion criteria will be considered as relevant protocol deviations. Non-programmable relevant eligibility and on-treatment protocol deviations, as well as significant (both programmable and non-programmable) eligibility and on-treatment protocol deviations will be reported through ClinSIGHT listings.

At Entrance:

- Subjects with ECOG PS > 1.
- Subjects with Child-Pugh B or higher.
- Subjects without evaluable disease at baseline.
- Subjects who received prior systemic therapy.
- Subjects with serum albumin < 2.8 g/dL.

- Subjects with total bilirubin > 3 mg/dL.
- Subjects with AST > 5 times the institutional upper limits of normal.
- Subjects with ALT > 5 times the institutional upper limits of normal.
- Subjects with co-infection of HBV and HCV.
- Subjects with co-infection of HBV and HDV.

On-study:

- Subjects receiving concurrent anti-cancer therapy (defined as chemotherapy, systemic therapy, radiation therapy, non-systemic therapy for HCC (local only), and surgery for HCC).
- Subjects treated differently as randomized (subjects who received the wrong treatment, excluding the never treated).

A by-subject listing will also be produced.

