#### **3.4.1.5 Palliative Local Therapy**

Palliative local therapy for clinically symptomatic tumor sites (eg, bone pain), including palliative (limited-field) radiation therapy and palliative surgical resection may be considered if the following criteria are met:

- The subject is considered to have progressed at the time of palliative local therapy and meets the criteria to continue with treatment beyond progression. ([Section 3.1.6](#))
- The lesion for palliative local therapy is a non-target lesion.
- The case is discussed with the BMS Medical Monitor prior to the initiation of palliative local therapy.

The potential for overlapping toxicities with radiotherapy and nivolumab currently is not known; however, anecdotal data suggests that it is tolerable. As concurrent radiotherapy and nivolumab have not been formally evaluated, in cases where palliative radiotherapy is required for a tumor lesion, then nivolumab should be withheld for at least 1 week before, during, and 1 week after radiation. Subjects should be closely monitored for any potential toxicity during and after receiving radiotherapy, and AEs should resolve to Grade < 1 prior to resuming nivolumab.

Tumor lesions requiring palliative local therapy should be evaluated for objective evidence of disease progression prior to the initiation of such therapy.

Palliative therapy must be clearly documented in the source records and electronic case report form. Details in the source records should include: dates of treatment, anatomical site, dose administered and fractionation schedule, and adverse events.

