### **3.4.2 Prohibited and/or Restricted Treatments**

#### **3.4.2.1 All subjects**

The following are prohibited for all subjects during the study:

- Loco-regional therapy for HCC
- Any concurrent antineoplastic therapy such as chemotherapy, molecular targeted therapy, hormonal therapy, immunotherapy, botanical formulations with an approved indication for cancer treatment (eg, traditional Chinese medicines) radiation therapy (except for palliative radiation therapy described in [Section 3.4.1.5](#))
- Immunosuppressive agents (except to treat a drug-related adverse event)
- Investigational agents for the treatment of cancer

Supportive care for disease-related symptoms may be offered to all subjects on the trial.

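### SAP 7.2.2 counts protocol-permitted palliative radiation and resection as a relevant protocol deviation

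*SAP*

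**What the plan says.** SAP 7.2.2 lists programmable items that are to be treated as relevant protocol deviations. One of its two on-study items is "Subjects receiving concurrent anti-cancer therapy (defined as chemotherapy, systemic therapy, radiation therapy, non-systemic therapy for HCC (local only), and surgery for HCC". No qualifier follows. On reporting, the section says: "The relevant protocol deviations will be summarized for all randomized subjects, by treatment group and overall". A by-subject listing is added. Non-programmable relevant deviations, and all significant deviations, go to ClinSIGHT listings.

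Protocol 3.4.1.5 concerns palliative local therapy for clinically symptomatic tumor sites, "including palliative (limited-field) radiation therapy and palliative surgical resection may be considered if the following criteria are met". Three criteria are then listed:

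- "The subject is considered to have progressed at the time of palliative local therapy and meets the criteria to continue with treatment beyond progression";
- "The lesion for palliative local therapy is a non-target lesion";
- the case has been discussed with the sponsor's Medical Monitor beforehand.

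Protocol 3.4.2.1 bans concurrent antineoplastic therapy for all subjects but words the radiation item as "radiation therapy (except for palliative radiation therapy described in" Section 3.4.1.5. The same section bans loco-regional therapy for HCC. Protocol 3.1.6 also mentions that palliative local therapy may be permitted after progression, following discussion with the Medical Monitor.

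**The concern.** The SAP item covers the same ground as the ban in Protocol 3.4.2.1 but leaves out the exception attached to that ban. A subject who is irradiated for pain at a non-target site after progression, stays on study drug and meets every criterion of 3.4.1.5 has not deviated, yet the programmed rule flags that subject.

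A reader uses this row to see how many subjects in each arm received anti-cancer therapy that the protocol forbids. If permitted palliation is mixed with real breaches, such as irradiation of a target lesion, the row no longer answers that question. The over-count also need not be equal between arms. Treatment beyond progression is open to both arms but depends on investigator-assessed benefit in an open-label trial. Neither the direction nor the size of any imbalance can be told from the documents.

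**Working it through.** The plan states no figure on this point that could be reproduced. The check is a comparison of texts, followed by a scale calculation.

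**Comparison by type of therapy**

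| Therapy during study treatment | Protocol | SAP 7.2.2 as written | Agree? |
|---|---|---|---|
| Palliative limited-field radiation meeting 3.4.1.5 | Permitted in 3.4.1.5 and exempted by name in 3.4.2.1 | Deviation | No |
| Palliative resection meeting 3.4.1.5 | Permitted in 3.4.1.5; surgery is not named in 3.4.2.1 | Deviation | No, but the permission rests on 3.4.1.5 alone |
| Radiation or resection of a target lesion, before progression, or otherwise outside 3.4.1.5 | Not permitted by 3.4.1.5 | Deviation | Yes |
| Other loco-regional therapy for HCC | Banned in 3.4.2.1 | Deviation | Yes |

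The conflict is confined to the first two rows and is clearest in the first.

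**Is the exception supplied elsewhere?** The SAP text available contains none, in 7.2.2 or in any other section. The next item in the same list, on subjects treated differently from their randomized arm, does carry a written exclusion (the never-treated). Exclusions are therefore stated in this list where they are intended, and a programmer has no basis for inferring one here.

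**Does the flag reach the efficacy analyses?** SAP 6.3 says of randomized subjects: "This is the type of subjects for analyses of study conduct, study population and efficacy". The SAP defines no per-protocol population, and no OS, ORR or PFS test uses the deviation flag. The effect stops at the deviation summary and its listing.

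**Scale.** Inputs: 363 subjects per arm and 726 in total (Protocol 3.1, SAP 2.1). The proportion *r* given palliative therapy that meets 3.4.1.5 does not appear in the documents. A range of 1% to 5% is assumed for illustration only.

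False deviations = *r* × number of subjects.

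| Assumed *r* | Per arm (363) | Total (726) |
|---|---|---|
| 1% | 0.01 × 363 = 3.63 | 0.01 × 726 = 7.26 |
| 5% | 0.05 × 363 = 18.15 | 0.05 × 726 = 36.3 |

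Using the same *r* in both arms is a simplification with no support in the documents.

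**The case against.** The strongest case on the other side is that this is housekeeping. It runs as follows.

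- **No conclusion depends on it.** That is correct, and it limits the severity. It does not make the count right.
- **A broad programmed screen backed by listings is a reasonable choice.** Two of the listed criteria, non-target lesion and prior discussion with the Medical Monitor, are hard to program, and 7.2.2 reports significant deviations separately. But the listings and the significant category do not alter the programmed row, which is what the summary shows by arm.
- **The SAP does not define concurrent.** Protocol 3.4.1.5 has nivolumab withheld for at least a week before, throughout and for a week after palliative radiation. Programming against dosing dates might therefore miss compliant nivolumab cases. The ambiguity is real. However, Protocol 3.4.2.1 needs its exception only because such radiation would otherwise count as concurrent, which supports the wider reading. A narrow reading would also treat the arms differently, because 3.4.1.5 states no such pause for sorafenib.
- **Protocol 3.1.6 is looser than 3.4.1.5.** It repeats neither the symptomatic nor the non-target condition. Section 3.4.1.5 is the more specific text and refers back to 3.1.6, so it is the sensible reference for an exception.
- **The numbers have no anchor.** This stands: they show scale and are not an estimate.
- **The change comes late.** SAP version 4.0 is dated 18 May 2020, after the database lock of 5 June 2019. This also stands, and it affects how the correction should be made.

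**Conclusion.** The concern holds. Read literally, SAP 7.2.2 classifies protocol-compliant palliative radiation and resection as relevant deviations. The conflict is explicit for radiation; for resection it rests on Protocol 3.4.1.5 alone. The conclusion assumes that the item is programmed as worded and that concurrent has the sense it carries in Protocol 3.4.2.1.

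The true over-count is unknown. Under the assumed 1% to 5% it is about 3.6 to 18.2 subjects per arm, or 7.3 to 36.3 overall. The OS, ORR and PFS analyses are not affected. This is a minor correction that is worth making.

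**What to change.** Add to the SAP 7.2.2 item: *excluding palliative radiation or palliative resection that meets Protocol Section 3.4.1.5*. Alternatively, report such therapy on its own line, labeled as not a deviation. Continue to count local therapy to a target lesion, before progression, or otherwise outside 3.4.1.5. If the table has already been produced, a split row or a footnote does the same job.

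The timing of the therapy against progression and study drug can be programmed where the dates are in the database. Target-lesion status and the Medical Monitor discussion can go through the route for non-programmable deviations that 7.2.2 already has.

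No new data collection should be needed, since the protocol requires: "Palliative therapy must be clearly documented in the source records and electronic case report form". Dates and anatomical site are specified there for the source records. The protocol text does not say which of these fields the eCRF holds, so some look-up in source may be required. The cost is one clause, a small programming change, and manual matching of treated sites to target or non-target lesions for the subjects concerned.

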7.3 Study Population

Unless otherwise specified, efficacy analyses will be performed on randomized subjects with treatment group as randomized; safety analyses will be performed on treated subjects with treatment group as treated.

7.3.1 Subject Disposition

The total number of subjects enrolled (randomized or not randomized) will be presented along with the reason of not being randomized.

Number of subjects randomized but not treated along with the reason will be tabulated by treatment group as randomized. This analysis will be performed only on randomized subjects only.

Number of subjects who discontinued treatment along with corresponding reason will be tabulated by treatment group as treated.

A subject listing for all enrolled subjects will be provided showing the subject's consent date, reason for not being randomized, and reason for not being treated.

A subject listing for all treated subjects will be provided showing the subject's randomization date, first and last dosing date, off treatment date and reason for going off-treatment.

7.3.2 Demographics and Other Baseline Characteristics

The following baseline characteristics will be summarized by treatment group as randomized. All baseline presentations identify subjects with missing measurements. Listings will also be provided.

